## Statistical methods

Statistical assessments of dosage normalized levodopa AUC0-inf, AUC0-last, AUC0-16, AUC0-2, AUC2-16, and AUC8-16 by analysis of variance (ANOVA) will be made on the logarithmic values, with back-transformation to nominal values of point estimates and confidence interval (CI). These variables will also be tested with dosage un-normalized values. The terms to be used in the ANOVA model will be sequence, patient within sequence, period, and formulation (i.v. or s.c. Infudopa and Duodopa; test and reference, respectively).

The statistical method for testing relative dosage normalized levodopa bioavailability will be based on the 90% CI for the ratio of the population means (test/reference). These statistical tests will also be done with dosage un-normalized values. The acceptance range for AUC ratio of the 90% CI for levodopa will be 0.80 to 1.25. These tests will be performed for Infudopa i.v. or Infudopa s.c. vs. Duodopa comparison.

The COV (coefficient of variation or % standard deviation; SD) will be calculated for each individual for plasma concentration between 2 and 16 h by dividing the SD for each individual curve with the mean value of plasma concentration between 2 and 16 h. The mean value of plasma concentration will be calculated for each curve as AUC2-16/14. Basic statistics for the COV will then be calculated per treatment group. The one-sided 90% CI of the intersubject COV will be calculated for Treatment 1 (i.v.) and Treatment 2 (s.c.) vs. Treatment 3 (Duodopa; reference) comparison, and for Treatment 1 (i.v. reference) vs. Treatment 2 (s.c.). It will also be tested with paired t-tests if there are significant differences in intersubject COV between treatments (i.v. vs. Duodopa, s.c. vs. i.v., and s.c. vs. Duodopa).

The level of significance will be p=0.05.

Clinical Study Protocol	Study code:	IPO-001
	Version No:	5.1
	Date:	26 MARCH
		2019

Safety will be summarized with the standard set of AE summary tables, and descriptive summary statistics of vital signs by visit and change from baseline. Local tolerability will be presented with descriptive summary statistics by visit and change from baseline.

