There is no reason to believe that Infudopa would exhibit any additional systemic adverse reactions than those described for other levodopa/carbidopa products, as summarised in the product information for Duodopa (see Investigator's Brochure). Duodenal administration of Duodopa has, however, a high risk of device- and procedure-related adverse reactions, such as postoperative wound infection, excessive granulation tissue, and incision site erythema, each reaction affecting more than 10% of patients (see Investigator's Brochure).

There is a potential risk of local adverse reactions at the administration site following Infudopa, however, local tolerance study in rabbits indicate that this risk should be low, and the reaction only short-term and not severe. However, the interim analysis of 5 patients showed that s.c. administration was associated with hematoma and transient and moderate pain or discomfort. Based on literature data, it was concluded that this was most likely due to the relatively high osmolarity caused by the high citrate concentration of the solution. Thus, when the trial starts again, a new buffer composition named Infudopa Buffer SubC, with a citrate concentration of only 20% of the previous one, will be used for the s.c. administration.

The half-life in plasma is short for levodopa, meaning that a lowering in pump rates following all routes of studied administration will quickly adjust down the levels of levodopa in plasma should, for example, dyskinesia occur. The clinical study is conducted at a phase I centre with intense monitoring of the patients that further reduces the risks. Please also refer to section 6.2 in the clinical study protocol for study dose and study design rationales. Data from the interim analysis have also given information allowing a fine tuning of the dosages.

When the study starts again, there will be a new interim analysis of pharmacokinetics (PK) and safety data after 4 of 18 (or 22 considering also possible compensatory patients) completed patients, after which a monitoring committee will meet to discuss the results and conclude if the study should continue, be modified with respect to design or discontinued. Evaluation will include blood PK samples, inspection of local dermal area/scoring including photos, and adverse events.

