### Table 2. Assessment schedule, Treatment Visits

Day within visit	-1											1													2		
Time point (h)	after noon	Pre dose	0	15 min	30 min	1	1,5	2	2,5	3	3,5	4	5	6	7	8	9	10	12	14	16	16,5	17	17,5	18	23	24
Vital Signs	х	х																									
Pregnancy Test (for females)	х																										
Randomization 	x																										
In-/exclusion criteria 	x																										 
Previous / concomitant treatment	x																										
Use of per protocol drugs for levodopa abstinence	х	х																			х	х	х	х	х	х	х
Treatment			х	х	х	х	х	х	х	х	х	х	х	х	х	х	х	х	х	х	х						
Inspection of local dermal area/scoring	х							х								х					х						х
Photo of local dermal area	х																										х
Food 							х					х				х			х								х
Adverse Events 	х	х	х	х	х	х	х	х	х	х	х	х	х	х	х	х	х	х	х	х	х	х	х	х	х	х	X5
Video recording 		х					х						х	х	х					X6							
PKG		х	х	х	х	х	х	х	х	х	х	х	х	х	х	х	х	х	х	х	х	х	х	х	х	х	х
Blood PK samples 			х	х	х	х	х	х	х	х	х	x	х	х	х	х		х	х	х	х	х	х	x	х	x	х
Laboratory Tests 																											X 

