#### 3.3.7. Inspection of local dermal area/scoring including photos

Inspection of local dermal area, including adverse event scoring, and photos will be performed at the site in Gothenburg at day -1 and day 2 during the treatment visits. The same assessments will be made at the Infudopa s.c. follow-up visit and the End-of-Study visit by the local Investigator. In addition to visual inspection and photo documentation of the skin area the area will be assessed for increased subcutaneous consistency, tenderness and pruritus (itching). Pain, tenderness and itching, respectively, will be rated by the subject using a horizontal 10 cm visual analogue scale (VAS) (Furue et al, 2013 and Younger et al, 2009). In the event of any occurrence of noduli or increased subcutaneous consistency, it will be photographed, and then the approximate borders will be delineated on the skin with a pen and photographed.

Photos will always be taken at day -1 and day 2 of each treatment visit according to provided instructions, and to document any abnormalities at the Infudopa s.c. follow-up visit, and at the End-of-Study visit. Photos of the skin area will be taken using a dark background behind the subject.

Perpendicular artificial lighting will be used and the subject will be asked to relax muscles. The subject will be photographed in dorsal recumbent position on all occasions. A 10 cm paper ruler tag will be placed at on the skin at the side of the infusion site and the full length of the ruler included in view. The subjects face or other identifiable features will not be included.

The photos will be assessed and scored according to the Draize Score (refer to Appendix B) by two blinded and independent dermatologists, and photos will be randomized between time, subjects and treatments for the assessment. The assessors will be trained before the study, and the order of the photos will be broken when all assessments are finalized. Estimation of area of the affected skin will be made, using the above-mentioned ruler as a calibration unit.

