The local tolerability will be documented with photographs, which will be evaluated by a dermatologist. Pre-defined local tolerability AEs will be documented by the investigator, and tenderness and pruritus with VAS by the subjects. Local tolerability will be presented with descriptive summary statistics of these variables by visit and change from baseline.

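### Section 8.2 leaves the pain VAS out of the local tolerability summary, and the Day -1/Day 2 timing in Section 3.3.7 conflicts with Tables 1 and 2

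*Protocol*

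**What the plan says.** **What is collected.** Section 3.3.7: "Pain, tenderness and itching, respectively, will be rated by the subject using a horizontal 10 cm visual analogue scale (VAS". That is three subject-rated scores.

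**What is to be summarised.** Section 8.2 names the dermatologist's evaluation of photographs, then "Pre-defined local tolerability AEs will be documented by the investigator", and then "tenderness and pruritus with VAS by the subjects". It closes with "Local tolerability will be presented with descriptive summary statistics of these variables by visit and change from baseline". Pain is not among the VAS items. The synopsis (Statistical methods) has a looser version without a list of items: "Local tolerability will be presented with descriptive summary statistics by visit and change from baseline".

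**When the skin is inspected and scored.** The opening of Section 3.3.7 says that inspection, adverse event scoring and photos "will be performed at the site in Gothenburg at day -1 and day 2 during the treatment visits". Table 1 marks inspection and scoring on Day -1, Day 1 and Day 2. The row "Inspection of local dermal area/scoring" in Table 2 is marked on the afternoon of Day -1 and at 2, 8, 16 and 24 h. Section 3.2 (Visits 2, 3 and 4) says that inspection and scoring follow Tables 1 and 2.

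**What the interim found.** Section 1.4: "s.c. administration was associated with hematoma and transient and moderate pain or discomfort". The s.c. buffer was changed in response.

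**The concern.** Section 8.2 gives an itemised list that disagrees with the protocol's own data collection. An analyst who follows it literally would not tabulate the pain VAS. Local tolerability at the injection sites is the focus of the first secondary objective (Section 2.2), and pain or discomfort is one of the two local findings from the first five patients.

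Timing adds to this. Pain described as transient may have passed by the morning after the infusion. Staff who schedule from the opening of Section 3.3.7 and staff who schedule from Table 2 would score the skin at different times, and no section says at which of those times the VAS is completed. A summary by visit does not by itself ensure that values obtained during infusion are shown.

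**Working it through.** No sample size, power or error rate is involved, so the check sets the texts side by side.

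**Step 1: the scores.**

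| Item rated by VAS | Collected (3.3.7) | Named for summary (8.2) |
|---|---|---|
| Pain | yes | no |
| Tenderness | yes | yes |
| Itching / pruritus | yes | yes |

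Three are collected and two are named: 3 − 2 = 1 omitted, and it is pain.

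**Step 2: does pain reach the summary another way?** Yes, in part. Later text in Section 3.3.7 includes pain among the pre-defined local symptoms that staff assess and rate for severity at the pre-defined time points. Pre-defined local adverse events are in the 8.2 list. Section 7.1.1 also allows infusion site pain as an adverse event term. Adverse event severity has three grades (mild, moderate, severe), whereas the VAS is a 10 cm scale completed by the subject. The loss is therefore the finer, subject-reported measure.

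**Step 3: the inspection times.**

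| Time in a treatment visit | 3.3.7, opening | Table 2 |
|---|---|---|
| Day -1 | yes | yes |
| 2 h | no | yes |
| 8 h | no | yes |
| 16 h | no | yes |
| Day 2 (24 h) | yes | yes |

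The Table 2 times were read by column position. The same reading puts the Food row at 1.5, 4, 8 and 12 h, which agrees with the meal times in Section 3.2. Table 2 therefore has five inspections per treatment visit against two in the opening of Section 3.3.7; the difference is 2, 8 and 16 h. Table 1 supports Table 2 by marking Day 1. Photos are at Day -1 and Day 2 in both text and tables, so they are not in conflict.

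**Step 4: which timing governs?** Section 3.2 points to the tables, and Section 3.3.7 itself later refers to pre-defined time points without listing them. The tables are thus operative and the on-infusion inspections remain in the plan.

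**Step 5: the VAS.** Section 3.3.7 gives the VAS no times of its own beyond the days in its opening, and Table 2 has no VAS row. If the VAS follows that opening, the only rating after the start of dosing within a visit is at about 24 h. With a 16 h infusion, that is 24 − 16 = 8 h after the pump stops. If it follows the inspection row, there are also ratings at 2, 8 and 16 h. The protocol does not settle which applies.

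**The case against.** The strongest reply is that this is editorial. Pain remains a pre-defined, severity-rated local symptom; Section 8.2 keeps pre-defined local adverse events and the standard adverse event tables; the synopsis does not restrict the items; and Section 6.2 makes local tolerability scores secondary variables without excluding pain. The outputs are descriptive, and a statistical analysis plan that is not shown could list every item. Section 3.2 sends staff to the tables. The interim Board reviews skin inspection and scoring and adverse events (Section 8.4), so its work does not depend on the summary sentence in 8.2.

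Most of this stands, and it rules out three stronger readings that a reader might infer:

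- **That s.c. pain would go unreported.** The adverse event route in Step 2 shows otherwise.
- **That the 2, 8 and 16 h inspections are lost.** That needs one sentence of Section 3.3.7 to be read against Section 3.2, both tables and later text in the same section.
- **That the trial could not show whether the new buffer helped.** Comparing buffers is not an objective, pain adverse events remain available, and the s.c. dosing basis also changed after the interim (Sections 1.3 and 5.1.1). Nor does Section 1.4 rank pain above hematoma or say when the pain occurred.

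The reply does not remove the mismatch itself. Leaving detail to an analysis plan is acceptable; giving a list that omits a collected score is a different matter. The missing VAS times concern data collection, which an analysis plan cannot repair afterwards.

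**Conclusion.** The point holds, and it is minor. Followed as written, Section 8.2 omits one of three collected subject-rated scores, for a symptom seen at the interim and within the focus of the first secondary objective. The Day -1/Day 2 wording in Section 3.3.7 contradicts Table 1 (Day 1) and Table 2 (2, 8 and 16 h). The tables prevail through Section 3.2, so the inspections stand, but the VAS time points remain unstated, and a by-visit summary can hide a transient reaction during infusion.

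This rests on reading the closing sentence of the local tolerability text in 8.2 as referring to the items listed just before it, and on Table 2 having been read correctly by column. It does not assume that the interim pain arose during infusion; if it did, the timing gap matters more.

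**What to change.** 1. In Section 8.2, list pain, tenderness and pruritus as the VAS items.
2. In Section 3.3.7, reconcile the timing of inspection and scoring with Tables 1 and 2, leave photos at Day -1 and Day 2, and state whether the VAS is completed at the same times as the inspections.
3. In Section 8.2, summarise the local tolerability scores by time point, including the highest on-infusion score, as well as by visit. Reporting the highest score is a reporting improvement and not the correction of a contradiction.

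The cost is wording and slightly more tabulation. The inspections are already scheduled. If VAS ratings were not intended at 2, 8 and 16 h, the change also adds brief ratings at those existing contacts.

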## 8.3. Pharmacokinetic analysis

The population for PK analysis will be all subjects with analysable PK parameters for at least 2 treatment visits during Day 1 and 2. Levodopa and carbidopaplasma profiles over time and PK parameter values will be summarized by regimen with descriptive statistics and graphically for Day 1 and 2.

The major pharmacokinetic variables, that will be calculated for levodopa (LD), carbidopa (CD), and 3-OMD are found in Table 8 below.

	Study code:	IPO-001
Clinical Study Protocol	Version No:	5.1
	Date:	26 MARCH 2019

Parameter	Description/derivation	Substance
		20000000
C max	The maximum observed concentration; obtained directly from the plasma concentration vs. time data	LD, CD, 3- OMD
t max	The time of the maximum observed plasma concentration.	LD, CD, 3- OMD
Cmin	The minimum (or trough) plasma concentration during the 2-16 h dosing interval, directly obtained from the experimental data of plasma concentration versus time, without interpolation	LD, CD, 3- OMD
AUC 0-16	The area under the plasma concentration versus time curve, calculated from time 0 to 16 hours, computed using the log-linear trapezoidal rule (method of the lin-up log down trapezoidal rule).	LD, CD, 3- OMD
AUC 2-16	The area under the plasma concentration versus time curve, calculated from time 2 to 16 hours, computed using the log-linear trapezoidal rule (method of the lin-up log down trapezoidal rule).	LD, CD
AUC 0-2	The area under the plasma concentration versus time curve, calculated from time 0 to 2 hours, computed using the log-linear trapezoidal rule (method of the lin-up log down trapezoidal rule). This represents the time period during the dosage interval when early onset of plasma concentrations are most representative.	LD, CD
AUC 8-16	The area under the plasma concentration versus time curve, calculated from time 8 to 16 hours, computed using the log-linear trapezoidal rule (method of the lin-up log down trapezoidal rule). This represents the time period during the dosage interval when apparent steady-state conditions of plasma concentration will be reached.	LD, CD
Clast	Last determinable plasma concentration	LD, CD, 3- OMD
AUC 0-last	The area under the plasma concentration versus time curve, calculated from time 0 to the last quantifiable plasma concentration ( $C_{last}$ ), computed using the log-linear trapezoidal rule (method of the lin-up log down trapezoidal rule).	LD, CD, 3- OMD
t½	Elimination half-life determined from the terminal slope of the log-linear curve	LD, CD
AUC 0-inf	The area under the plasma concentration versus time curve, calculated from time 0 to infinity, computed using the log-linear trapezoidal rule (method of the lin-up log down trapezoidal rule) including the rest AUC from the last quantifiable sampling point up to infinity (calculated using C last and the elimination slope).	LD, CD
Cav	The average plasma concentration at the steady-state = $AUC_{8-16}/8$	LD, CD
PTF	The peak-trough fluctuation = $(C_{max}-C_{min})*14/AUC_{2-16}$	LD, CD

Table 8. Pharmacokinetic variables est	timated during Day 1 to 2
--	---------------------------

PK variables will be calculated based on the actual sampling times rather than the scheduled sampling times.

If there is a baseline plasma concentration of levodopa and carbidopa that is >LLOQ this concentration value will be subtracted from the actual plasma concentration value at baseline, and subsequent concentration values assuming an elimination of the substances that is in accordance with the subject's own elimination rate (calculated from 16 h and up). This will be made until the so calculated subtraction value is insignificant (i.e. < LLOQ). No such baseline correction will be made for 3-OMD.

	Study code:	IPO-001
Clinical Study Protocol	Version No:	5.1
	Date:	26 MARCH 2019

Bioavailability will be calculated in the cross-over design on dosage normalized levodopa and carbidopa  $AUC_{0-inf}$ ,  $AUC_{0-last}$ ,  $AUC_{0-2}$ ,  $AUC_{0-2}$ , and  $AUC_{8-16}$  for test versus reference by using the logarithmic values, with back-transformation to nominal values of point estimates (cf. Section 8.2).

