There is no documentation available showing the levodopa bioavailability for Duodopa vs. the i.v route. Based on the needed dosages of a levodopa solution administered i.v. to patients previously treated with Duodopa at the Linköping University Hospital, it may be estimated that Duodopa administered enterally is about 75% bioavailable as compared to i.v. administration. Experience from patients following s.c. administration at the same center suggests that equal doses of s.c. and Duodopa administrations can be used (Dizlin, data onfile). This suggested that the bioavailability of s.c. formulation may be in the range 75-100% when considering a complete dosage interval of a day. The dosage calculations for s.c. administration when starting the trial was hence based on the assumption of a 75% bioavailability. Analysis of data from the first 5 interim analysis patients, however, revealed that the absolute bioavailability of Infudopa s.c. is 100% vs. the i.v. standard, i.e. higher than expected (Clinical Study Interim Report 2019-01-15). Also Duodopa had a slightly higher absolute bioavailablity than the previous estimation (82% vs. i.v.). The ratio between LCIG and s.c. Infudopa levodopa bioavailability based on AUC 0-infinity was 0.78 and based on AUC 0-16 h 0.86. The AUC 0-16h was regarded as the most relevant variable for dose adjustment, because this is the time interval when the patient needs the optimal effect. Hence it was decided, that for the second part of the trial the dosage of Infudopa s.c. will be based on the assumption of an 86% bioavailability of Duodopa as compared to Infudopa s.c..

The aim of the present study will be to compare the pharmacokinetic and safety profile of Infudopa administered i.v. and s.c. with Duodopa administered enterally in patients with late stage Parkinson's disease.

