## 3. STUDY DESIGN AND PROCEDURES

## 3.1. Overall study design and flow chart

This is a prospective, randomized, 3-period cross-over, open-label multicentre trial. Patients fulfilling all of the inclusion and none of the exclusion criteria will be randomized to one of the three treatment arms. There have been 5 interim patients already studied. Enrolment upon restart of the study will be continued until the required sample size is achieved (18 subjects in total entering the second part of the study, giving in total 23 subjects in the study). Once informed consent is

[figure not shown]
	Study code:	IPO-001
Clinical Study Protocol	Version No:	5.1
	Date:	26 MARCH 2019

obtained, screening data will be collected to determine each patient's eligibility for study participation.

The duration of subject participation in the study is expected to be around 3-4 months from screening to final follow-up (with variation depending on subject's availability between treatment visits), and the subject will be on study treatment for in total 3 days.

Patients with Parkinson's disease who are on Duodopa treatment because of severe on- off manifestation when on oral levodopa will be identified and recruited by experienced neurologists at neurology clinics at university hospital clinical sites in Sweden. Patients will travel from their living location to a clinical phase I site with full Good Clinical Practice (GCP) standard at the Sahlgrenska University Hospital in Gothenburg for the three treatment visits.

The subjects will be assessed at the phase I study clinic, where they during one treatment visit will receive Duodopa at optimal dosage for 16 hours, during another treatment visit will receive i.v. Infudopa at a concentration estimated to yield corresponding serum levels of levodopa for the same duration, and at a third treatment visit will again receive the corresponding amount of levodopa but in the form of s.c. Infudopa. The study will hence have a cross-over design with a minimum of three days on Duodopa between the different treatment visits, where the order of treatments will be non-blinded but randomized.

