#### Table 4. Product identity

#### 5.1.1. Doses and treatment regimens

All dosing during the study will be based on the patient's *regular day time hourly dose-requirement of Duodopa*. This consists of the regular continuous Duodopa dose (mg), plus the average accumulated daily extradoses (mg) divided by the regular daily infusion time (h). The morning Duodopa bolus dose is for the study set to 110% of the *regular day time hourly dose-requirement of Duodopa*. Consequently the *pre-study daily Duodopa dose* is for this study defined as:

The regular day time hourly dose-requirement  $\times$  (16 h – morning bolus infusion time h) + 110% of the regular day time hourly dose-requirement of Duodopa.

The total dose per day will be the sum of two components: morning bolus dose, and continuous (maintenance) dose given over a 16-h period. The combined i.v. infusion of Infudopa Active with Infudopa Buffer IntraV will be named Infudopa IntraV, and the combined s.c. infusion of Infudopa Active with Infudopa Buffer SubC will be named Infudopa SubC. In the following text doses and treatments apply to subjects in the second phase of the study (n=18). Before the start of this phase, it was decided that the bolus doses should be determined by a fixed percentage of the continuous hourly dose. The percentage chosen was for Infudopa IntraV 110%, for Infudopa SubC 155%, and for LCIG 110%. If clinically justified in the individual patient, the bolus dose may be adjusted, maintaining the relation 1 : 1.4 : 1 between the bolus doses for the different administration modes i.v : s.c : intestinal. The total dose is adjusted for the relative bioavailability based on AUC during the 0-16 h dosage interval vs. LCIG that was found in the interim study (ratio LCIG/Infudopa IntraV = 0.81; ratio LCIG/Infudopa SubC = 0.86).

Clinical Study Protocol		Study code:	IPO-001
	Clinical Study Protocol	Version No:	5.1
		Date:	26 MARCH 2019

Treatments will comprise the following therapy, where treatment 1 and 2 are considered investigational, and treatment 3 reference therapy:

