### 8.4. Interim analysis

There has been an interim analysis of first 5 subjects in the study (Clinical Study Interim Report 2019-01-15). There will be a new interim analysis of PK and safety data after 4 completed subjects after the study has re-started. The number of 4 subjects for the interim analysis is because it will allow for reasonably adequate mean values of numerical variables and frequencies of distribution of binominal variables, including reasonable estimates of confidence intervals. The following data will be included in the interim analysis (see Table 1 and 2):

- Blood PK samples
- Inspection of local dermal area/scoring incl. photos
- Adverse events

A Board of the Interim Study Analysis will meet to discuss the results and conclude if the study should continue or not.

The possible outcomes the Board will evaluate, and the basis for the decisions are:

1. Are the plasma levels of LD following s.c. and i.v. too high or too low as compared to Duodopa at any time during the treatment, so a dosage adjustment is necessary? Decision rules:

- If the deviation from Duodopa is of a magnitude that is deemed clinically important, appropriate changes in the dosing protocol in the study will be considered.

- If the deviation from Duodopa at steady-state is larger than established limits for bioequivalence (80% - 125%), the appropriate changes in the dosing protocol will be made.

2. Is the local and systemic tolerance acceptable?

Decision rule:

If adverse events have occurred which, according to the committee, can be attributed to the study drug and make it ethically unjustifiable to pursue the trial, the trial will be stopped. However, the trial can continue after the appropriate changes have been made if it can be convincingly demonstrated that changes in the protocol, e.g. a change of infusion rate, infusion system, an increase in the number of subcutaneous infusion sites or other feasible actions, will mitigate the risk for further adverse events.

In case the dosage regimen is changed, or other major change is made to the Clinical Study Protocol (CSP) an amendment must be submitted to MPA and EC.

Only descriptive summary statistics will be performed. There will be no statistical hypothesis testing.

The members of the Board of the Interim Study Analysis are presented in Appendix C.

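### As written, the PK analysis set mixes five first-phase patients, treated with a since-replaced s.c. buffer and another dosing basis, with the second-phase patients

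*Protocol*

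**What the plan says.** - **Analysis set.** Protocol section 8.3: "The population for PK analysis will be all subjects with analysable PK parameters for at least 2 treatment visits during Day 1 and 2".
- **Who counts as a subject.** Section 8.4: "There has been an interim analysis of first 5 subjects in the study". Section 3.1: "18 subjects in total entering the second part of the study, giving in total 23 subjects in the study".
- **S.c. product.** Section 1.4 announces "a new buffer composition named Infudopa Buffer SubC, with a citrate concentration of only 20% of the previous one" for the restart.
- **S.c. dose basis.** Section 1.3 on the first phase: "The dosage calculations for s.c. administration when starting the trial was hence based on the assumption of a 75% bioavailability". On the second: "for the second part of the trial the dosage of Infudopa s.c. will be based on the assumption of an 86% bioavailability of Duodopa" relative to s.c. Infudopa.
- **I.v. dose and bolus.** Section 5.1.1 sets the i.v. dose at 81% from the interim ratio. Before the second phase it made the bolus a fixed percentage of the hourly dose (110% i.v., 155% s.c., 110% Duodopa). The same section confines its dosing text to the 18 second-phase subjects.
- **Analysis.** Section 8.2 fits sequence, patient within sequence, period and formulation. It tests dose-normalised AUC and, in addition, un-normalised AUC, both against 0.80 to 1.25. It compares the COV over 2-16 h between treatments and summarises local tolerability by visit, with no split by buffer.

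Section 5.1.1 restricts its text to the second phase. Section 8 has no matching restriction.

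**The concern.** The trial is meant to support the s.c. product and regimen now in use. Under the section 8.3 wording, about a fifth of the s.c. curves could come from a different buffer, dosing basis and bolus rule, with nothing in the model to show it.

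Dose normalisation answers only part of this. It rescales exposure for the amount given, but it cannot correct a change in how the drug is absorbed. The COV is already scale-free, so it cannot be adjusted that way at all. Section 1.3 reports that s.c. absorption of a similar solution is delayed by 2 to 3 h, so a changed buffer, or a changed bolus relative to maintenance, could alter the shape of the curve inside the 2-16 h window.

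Local tolerability has the same problem. Section 1.4 says the buffer was replaced because of haematoma and pain or discomfort in these five patients. An s.c. table that combines both buffers would not describe the current product.

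**Working it through.** **1. The plan's own sample size (section 8.1).** The stated inputs are COV 24.5% (cited Duodopa study), 23.8% (interim 17.0% raised by 40%), and Z values 1.96 and 0.84. A paired formula with a distance of 0.20 and a small-sample correction reproduces the stated figure:

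n = (COV × (1.96 + 0.84) / 0.20)² + 1.96² / 2

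- COV 24.5%: 11.76 + 1.92 = 13.69, so 14.
- COV 23.8%: 11.10 + 1.92 = 13.02, so 14.

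The 18 for the COV non-inferiority test cannot be fully checked, because no SD of the individual COVs is given. Taking it as stated, 18 + 4 drop-outs = 22. The needs of 14 and 18 are therefore met by 18 second-phase completers without the five.

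**2. Share of the set.** 5/(5 + 18) = 21.7%. If all 22 complete, 5/(5 + 22) = 18.5%.

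**3. Un-normalised s.c./Duodopa ratio.** The interim Duodopa/s.c. ratios (section 1.3) are 0.86 for AUC0-16 and 0.78 for AUC0-inf. The first-phase s.c. dose as a fraction f of the Duodopa dose is not stated. I assume 0.75 to 1.00, where 1.00 follows if both were taken as 75% bioavailable. The second-phase fraction is 0.86. Assuming no buffer effect:

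- first-phase ratio r1 = f / interim ratio
- second-phase ratio r2 = 0.86 / interim ratio
- pooled ratio = exp[(5 ln r1 + 18 ln r2) / 23]

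| AUC | f | r1 | r2 | pooled |
|---|---|---|---|---|
| 0-16 | 0.75 | 0.872 | 1.000 | 0.971 |
| 0-16 | 1.00 | 1.163 | 1.000 | 1.033 |
| 0-inf | 0.75 | 0.962 | 1.103 | 1.070 |
| 0-inf | 1.00 | 1.282 | 1.103 | 1.139 |

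The shift is about 3% either way (about 4% at f = 1.00 with only 14 second-phase subjects). For i.v., an assumed first-phase fraction of 0.75 gives 0.75/0.81 = 0.926 for AUC0-16, pooled with 1.00 to 0.983.

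**4. Effect on an interval.** In the least favourable row (AUC0-inf, f = 1.00), with a paired log-SD of 0.245, the 90% CI is 0.998-1.220 for the second phase alone (n = 18) and 1.043-1.243 pooled (n = 23). Both lie inside 0.80-1.25, the second only just.

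**5. Dose-normalised tests.** The dose factor largely cancels here, but a buffer effect would not. As a pure hypothetical, a second-phase ratio of 0.75 pooled with the interim 1/0.86 = 1.163 gives exp[(5 ln 1.163 + 18 ln 0.75) / 23] = 0.825. The pooled point estimate is then inside the range although that of the current product is outside.

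**6. Precision lost by restricting.** For a true ratio of 1 and log-SD 0.245, 90% CI = exp(± t × 0.245 / √n), with t on n − 1 degrees of freedom: 0.904-1.106 at n = 18 against 0.916-1.092 at n = 23.

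**The case against.** The section 8.3 sentence is a data-availability rule. It does not say that the phases are to be combined. The sample size of 18 plus 4, and the dosing text limited to 18, suggest a stand-alone second phase. The 23 in section 3.1 is a headcount, and an SAP may settle the matter. This stands as to intent: no sentence expressly puts the five in the final test. It does not cure the text, because the protocol does state a population and that population has no limit by phase.

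The quantified shifts concern the un-normalised tests, which are additional; the trial is sized on dose-normalised AUC0-inf. No section reports an effect of the buffer on absorption. Both points stand. However, the interim bioavailability ratios were obtained with the old buffer, so the protocol gives no ground for assuming that the effect is nil.

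Three stronger readings are tempting and not supported:

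- **Circularity.** The five patients supplied the 0.81 and 0.86 factors, so a reader might infer that including them lets the trial confirm its own doses. Their dose-normalised s.c./Duodopa ratios are 1/0.86 = 1.16 and 1/0.78 = 1.28, the latter above 1.25. Unless the second-phase ratio falls well below 1, as in the hypothetical of step 5, these values pull away from equivalence.
- **Excluding the five from everything.** The new buffer is for s.c. only, so the buffer argument does not reach the dose-normalised i.v. versus Duodopa comparison.
- **An automatic repeat after the second interim.** Section 8.4 makes a dose change only one possible outcome, implemented by amendment. A standing exclusion rule could cut the un-normalised set to 18 − 4 = 14.

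**Conclusion.** The point holds as a defect of wording with consequences for the s.c. comparison. Followed as written, section 8.3 admits five patients, 19% to 22% of the PK set, who had a different s.c. buffer, dose basis and bolus rule. Section 8.2 neither models study part nor separates tolerability by buffer.

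The part that can be quantified is modest: about 3% on the un-normalised s.c./Duodopa ratio, of unknown direction, resting on an assumed first-phase dose fraction of 0.75 to 1.00 and no buffer effect. Nothing here shows that an equivalence conclusion would change. A buffer or bolus effect on s.c. AUC and on the 2-16 h COV cannot be sized from the protocol. That is the main reason not to pool the two s.c. products in the confirmatory test.

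**What to change.** In section 8.3, state that the following use second-phase subjects only:

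- the confirmatory comparisons involving s.c. Infudopa, for AUC and for COV;
- all un-normalised AUC tests.

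Add one sentence to section 8.2 saying the same for the s.c. local-tolerability summaries. Report the five first-phase patients separately, with a pooled analysis as sensitivity.

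The dose-normalised i.v. versus Duodopa comparison may use both phases if study part is accounted for. It is best run as a separate model, so that first-phase s.c. curves do not enter. A main effect of study part alone would be absorbed by the patient terms, so the useful check is a study-part-by-formulation term.

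The cost is two sentences and the slightly wider interval in step 6. The planned 14 and 18 are still met, provided 18 second-phase subjects complete.
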